### Rates

The respective transfusion rates will be defined as the number of units in each period divided by the number of days in the period, i.e., ■ days before treatment and  $TD [days] = SD - DA$  ■ after first dose.

#### **7.7.3 Duration of treatment**

Duration of treatment (DoT, in days) will be defined as the time elapsed from the start of treatment (date of administration at cycle ■, week ■) to the date of treatment discontinuation (TD) or the last available date with drug administration (LD):

$DA$  ■ = Drug administration date in Visit ■ [YYYY-MM-DD]

$DoT [days] = \min(TD, LD) - DA$  ■

#### **7.7.4 Hematological response**

All patients with one of the following responses assessed by samples and procedures taken/carried out at visit ■ in cycle ■ are defined as responders (assessed through the combined response criteria for MDS and AML used in this trial (see section 11.2 Appendix 2)):

- [1] CR, CRi, PR as defined in section 11.2 Appendix 2 a )
- [2] Hematologic improvement (for one or several lines) as defined in section 11.2 Appendix 2 a )

If any of those criteria is fulfilled, the subject will be classified as responder. Otherwise, he will be classified as non-responder. Patients for whom the overall hematologic response cannot be determined will be considered as treatment failures.

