2.3 Study endpoints

2.3.1 Primary endpoint

The primary endpoint of the study is defined as overall hematological response rate as assessed in [REDACTED] of treatment with imetelstat.

All patients with one of the following responses assessed by samples and procedures taken/carried out at [REDACTED] are defined as responders (assessed through the combined response criteria for MDS and AML used in this trial (see Appendix III a), section 16.3):

[1] CR, CRi, PR as defined in Appendix III a)

[2] Hematologic improvement (for one or several lines) as defined in Appendix III a)

Response rate is calculated as follows: number of responders divided by the number of all patients of the analysis set. Patients for whom the overall hematologic response cannot be determined will be considered as treatment failures.

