5.1.3 Disease assessments in the primary phase of the treatment period (■■■■■)

After cycles ■ and ■ (i.e., at the beginning of cycles ■ and ■) response assessments will be carried out based on bone marrow and peripheral blood samples taken. For that, blood counts to assess potential cytopenias will be carried out and bone marrow and peripheral blood smears will be prepared to perform cytomorphology assessments.

Of these response assessments, the assessment at the end of ■■■■■ (performed at the beginning of cycle 5) is the primary endpoint (pEP) assessment.

Based on the outcome of the disease assessment in ■■■■■, if signs of disease progression are seen in the bone marrow, treatment with imetelstat will be stopped and the patient will undergo EOT and enter the follow-up phase.

Based on the outcome of the pEP (■■■■■) visit disease assessment, subjects will be either discontinued from treatment with imetelstat and enter the posttreatment follow-up phase (non-responders) or will continue treatment with imetelstat until loss of response/disease progression in the extension phase of the treatment period (responders) (see below at 5.1.4). In the absence of alternative treatment options, non-responders with stable or controlled disease may continue treatment in the extension phase at the investigator's discretion, in consultation with the sponsor, provided the disease remains controlled and none of the discontinuation criteria as described in section 7.7 are met. These subjects will follow the assessments and procedures according to the schedule of assessments for the extension phase (section VII, Part 2c). Responders who have BM blasts $\geq 5\%$ at the response assessment in cycle ■ will continue to receive imetelstat every ■ weeks. Responders who have BM blasts $<5\%$ at the response assessment in cycle ■ will continue to receive imetelstat every ■ weeks.

The disease assessment will be performed according to combined response criteria based on IWG 2018 criteria (MDS)¹ and the criteria of the European LeukemiaNet (AML)² in order to harmonize the criteria for MDS and AML patients in this trial. The combined criteria are listed in Appendix III a), section 16.3.

- Evidence of clinical benefit is defined as:
 - **At least partial remission (PR):**
 - This includes CR, CRi, PR and HI (any line) as per the combined response criteria used in this trial

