Progressive disease (PD)	Evidence for an increase in bone marrow blast percentage and/or increase of absolute blast counts in the blood: 
 >50% increase in marrow blasts over baseline (a minimum 15%-point increase is required in cases with <30% blasts at baseline; or persistent marrow blast percentage of >70% over at least 3 mo; without at least a 100% improvement in ANC to an absolute level ($>0.5 \times 10^9/L$ [500/μL], and/or platelet count to $>50 \times 10^9/L$ [50 000/μL] non-transfused); or >50% increase in peripheral blasts (WBC x % blasts) to $>25 \times 10^9/L$ (>25 000/μL) (in the absence of differentiation syndrome)†; or New extramedullary disease
Hematologic relapse (after CR, CR _i)	Bone marrow blasts $\geq 5\%$; or reappearance of blasts in the blood; or development of extramedullary disease
Hematologic improvement (HI)	
Erythroid response (HI-E)	
NTD (0 RBCs in 16 wk)*	At least 2 consecutive Hb measurements ≥ 1.5 g/dL for a period of minimum 8 wk in an observation period of 16 to 24 wk compared with the lowest mean of 2 Hb measurements (apart from any transfusion) within 16 wk before treatment onset‡; only a response duration of at least 16 wk, however, is considered clinically meaningful
LTB (3-7 RBCs in 16 wk in at least 2 transfusion episodes, maximum 3 in 8 wk)*	Transfusion independence, defined by the absence of any transfusions for at least 8 wk in an observation period of 16-24 wk with the same transfusion policy (defined below) compared with 16 wk prior to treatment; only a response duration of at least 16 wk, however, is considered clinically meaningful
HTB (≥ 8 RBCs in 16 wk, ≥ 4 in 8 wk)	
Major response: Major HI-E response in HTB patients corresponds to transfusion independence, defined by the absence of any transfusions over a period of minimum 8 wk in an observation period of 16-24 wk with the same transfusion policy (defined below) compared with 16 wk prior to treatment; only a response duration of at least 16 wk, however, is considered clinically meaningful
 
Minor response: Minor HI-E response in HTB patients is defined as a reduction by at least 50% of RBCs over a minimum of 16 wk with the same transfusion policy (defined below) compared with 16 wk prior to treatment

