## 6.2 Endpoints and Related Variables

### 6.2.1 Primary Endpoint

Objective	Endpoint
To assess the efficacy of imetelstat for the treatment of AML and MDS patients failing or being refractory to first line hypomethylating agent (HMA)-based treatment	Overall hematological response rate as assessed in week ████████ of treatment with imetelstat using the combined response assessment criteria for MDS and AML (see Appendix 11.2 for more details). The main analysis will be based on the eCRF item “Is the subject classified to be a Responder according to protocol?” (RS_DSRESP).

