#### 7.7.6 Progression-free-survival

Progression-free-survival (PFS) will be defined as the duration of time from time of treatment to time of progression or death, whichever occurs first. A subject who has neither progressed (defined as first time having Progressive disease (PD) or Progression or relapse after HI on response assessment) nor died will be censored on the date of the last observation. Therefore:

In case there was a progression or death:

PFS [days] = min(date of progression/death) – Drug administration date in Visit [REDACTED] +1

Otherwise, censoring date will be:

PFS [days] = date of last observation – Drug administration date in Visit [REDACTED] +1

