### 8.3 Evaluation of Primary Endpoint

The primary objective of this study is to assess the efficacy of imetelstat for the treatment of AML and MDS patients failing or being refractory to first line hypomethylating agent (HMA)-based treatment. This should be illustrated by testing the hypothesis stated in section 2.5 using the primary endpoint stated in section 6.2.1 (see 7.7.4 for derivation).

The absolute and relative frequencies of overall hematological response as assessed in week ■ (beginning of ■) of treatment with imetelstat will be evaluated using the FAS and repeated for the PPS if the analysis sets differ more than 10% between the number of included subjects. Treatment success will be determined by patients showing at least PR (CR, CRi or PR) and/or showing a hematologic improvement for one or several lines.

The primary analysis will be based on a Simon's two-stage design for an initial assessment of efficacy. Based on the study hypothesis (see section 2.5), an absolute cut-off value of ■ subject out of ■ will be used to determine if the study must be stopped for futility at the IA. For the final analysis in case the study proceeds, if final sample size is equal to the calculated one, a cut-off value of ■ subjects out of ■ will be fixed.

If final sample size is different from the calculated sample size (overrunning), uniformly minimum variance unbiased estimator UMVUE will be tested (see Melikov M. & Karanevich A. 2022) with a

model based on a binomial distribution conditioned to the first stage results and with an assumed expected true response rate of 0.2.

A SAS macro (based on source <https://www.lexjansen.com/pharmasug/2022/SA/PharmaSUG-2022-SA-123.pdf>) can be used for this analysis (see Appendix 11.4)

For the IA:

A binomial exact test will be performed with a two-sided 90% confidence interval for overall hematological response rate using the Clopper-Pearson method. A SAS pseudo code can be:

```
proc freq data=Data;
  tables Hematological_response / binomial(all level="0") alpha=0.1 cl ;
  exact binomial /point;
run;
```

For the final analysis:

The final analysis was going to be performed with a calculation of the p-value and a 90% confidence interval (two-sided, equivalent to a one-sided 95% confidence interval) for the UMVUE (see Melikov M. & Karanevich A. 2022).

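### The responder rule counts hematologic improvement without requiring progression to be absent, so a patient first meeting PD at visit 9 can be both a primary-endpoint responder and a PFS event

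*SAP*

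**What the plan says.** Protocol 2.3.1 defines the primary endpoint by two routes. The first is CR, CRi or PR. The second is "Hematologic improvement (for one or several lines) as defined in Appendix III a". SAP 7.7.4 repeats the second route as "Hematologic improvement (for one or several lines) as defined in section 11.2 Appendix 2 a" and joins the two by a plain OR: "If any of those criteria is fulfilled, the subject will be classified as responder". SAP 8.3 agrees: it counts as a success any patient who reaches PR or better, who has HI in some line, or who has both. The main analysis reads one eCRF item, RS_DSRESP, worded "Is the subject classified to be a Responder according to protocol" (SAP 6.2.1).

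In the combined criteria (protocol Appendix III a, SAP Appendix 2 a), stable disease is the only category conditioned on PD not being met. HI is defined on hemoglobin, transfusions, platelets or neutrophils and carries no such condition. PD has three limbs:

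- a rise or persistence of marrow blasts, with an exemption for sufficient ANC or non-transfused platelet recovery;
- a rise in peripheral blasts;
- "New extramedullary disease".

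For PFS, SAP 7.7.6 takes progression as "defined as first time having Progressive disease (PD) or Progression or relapse after HI on response assessment".

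On treatment, protocol 5.1.3 describes clinical benefit at the primary-endpoint assessment thus: "This includes CR, CRi, PR and HI (any line) as per the combined response criteria used in this trial". Protocol 7.7 lists disease progression among the reasons for discontinuation.

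**The concern.** The population has failed HMA-based therapy, and rising blasts are an expected course. If one blood line improves while blasts rise or extramedullary disease appears, the written rule makes the patient a primary-endpoint success. The same assessment is a progression event for PFS, and no precedence rule says which finding governs response.

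Two things are at stake. One is the meaning of the response rate, which is reported per cohort with an exact 90% interval. The other is consistency between sites: response is assessed locally by the investigator in an open-label trial, so an unwritten rule may be applied differently from site to site.

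**Working it through.** The documents state no figure for this overlap, so there is none to reproduce. The check is on the definitions, followed by the weight of one patient.

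**Step 1. Where HI and PD can coexist.** Inputs are the thresholds in Appendix III a) (platelets and ANC in 10⁹/L).

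- Marrow PD: blasts up by more than 50% over baseline, and by at least 15 points if baseline is below 30%. It is waived if ANC improves by at least 100% to above 0.5, and/or non-transfused platelets recover to above 50. I read the waiver as covering the whole marrow limb.
- HI-N: ANC up by at least 100% and by more than 0.5.
- HI-P: up by 30 if starting above 20; or from below 20 to above 20, and by at least 100%.

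| Patient at visit 9 | HI met? | Marrow PD waived? |
|---|---|---|
| ANC 0.4 → 1.0 | HI-N | Yes |
| Platelets 25 → 56, ANC 0.4 unchanged | HI-P (+31) | Yes (×2.24, above 50) |
| Platelets 60 → 95, ANC 0.4 unchanged | HI-P (+35) | Unclear: yes if above 50 is enough, no if doubling is also required |
| Platelets 10 → 25, ANC 0.4 unchanged | HI-P | No |
| Hemoglobin or transfusion response only, ANC and platelets unchanged (0.4 and 30) | HI-E | No |

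The HI-N row holds generally: if ANC at least doubles and rises by more than 0.5, it must end above 0.5, so the waiver always applies. The waiver does not mention hemoglobin or transfusions. It is not attached to the peripheral-blast or extramedullary limbs, so HI in any line can coexist with those.

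**Step 2. One patient in full.** Marrow blasts 20% → 45%, platelets 10 → 25, no ANC recovery.

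- Blasts: 45 − 20 = 25 points (at least 15), and 25/20 = 125% (more than 50%). Platelets end at 25, not above 50, so there is no waiver. PD is met.
- Platelets: from below 20 to above 20, and 15/10 = 150% (at least 100%). HI-P is met.
- SAP 7.7.4: responder. SAP 7.7.6, if this is the first PD: PFS event at the same assessment.

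**Step 3. Timing.** Marrow progression at the early assessment (visit 5) ends treatment (protocol 5.1.3 and 7.1). The overlap therefore mainly concerns PD first met at visit 9.

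**Step 4. Weight of one patient.** Cohort sizes are redacted, so n is an assumption.

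- n = 20: 1/20 = 5.0 points. n = 40: 1/40 = 2.5 points.
- Clopper-Pearson 90% at n = 20, with zero responders: the upper limit is 1 − 0.05^(1/20) = 13.9%, so 0/20 gives 0 to 13.9%.
- With one responder: the lower limit is 1 − 0.95^(1/20) = 0.3% and the upper limit is the 95th percentile of Beta(2, 19) = 21.6%, so 1/20 gives 0.3 to 21.6%.

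**The case against.** Several replies carry weight.

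- **HI is included on purpose.** The endpoint is a hematological response, and a count-based response and a blast-based progression are different constructs. Disagreement between endpoints is not in itself an error. That is fair, but the documents never say that HI should count despite PD. The overlap follows from a missing condition, not from a stated choice.
- **An investigator would answer no.** Possibly, and we cannot see whether the eCRF forces a single category. But the item asks about response according to protocol, and the protocol rule gives yes.
- **It would be visible.** Response assessments at visits 5 and 9 and marrow cytology are listed (SAP 8.3 and 8.5.4), so marrow overlap could be found. A listing does not settle how the patient is counted.
- **Nothing turns on it formally.** Protocol 10.1 and 10.8.1 make the analysis exploratory, so no decision against p0 = 0.05 now rests on it. The SAP document history records no responders at the interim. If HI was counted there, the overlap added no responder among the patients assessed then, and any effect is confined to later patients. This limits the consequence, although the response rate remains the primary result.

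A reader might also infer a direct contradiction on treatment, because HI in any line supports continuation (protocol 5.1.3 and 8.1.5) while PD is a discontinuation reason (7.7). The documents do not support it that strongly. Protocol 5.1.4 and 8.1.6 require extension-phase assessments to confirm absence of progression, which largely answers it. Those texts govern treatment, however, and are not carried into the endpoint derivation.

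**Conclusion.** The gap is real and should be fixed, but it is bounded. As written, the rule can count a patient who first progresses at visit 9 as a primary-endpoint responder while SAP 7.7.6 records a PFS event. This can occur with HI-E, with HI-P that does not meet the marrow-limb exemption, or with any HI combined with the peripheral-blast or extramedullary limb. It cannot occur between marrow-limb PD and HI-N, or between marrow-limb PD and HI-P that at least doubles to above 50 × 10⁹/L non-transfused.

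Two stronger readings are not supported. A reader might infer that the reported response rate will be materially inflated, but no frequency can be derived from the documents and it may be zero. The 2.5 to 5.0 points are per patient, under an assumed cohort of 40 down to 20. A reader might also take a mismatch with best overall response as further evidence. SAP 7.7.8 ranks categories by table order and HI stands last, so an HI responder with stable disease is displaced too. That is a separate matter and not a product of this overlap.

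**What to change.** Before database lock:

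1. In protocol 2.3.1, SAP 7.7.4 and SAP 8.3, reword the second route as: *hematologic improvement (one or several lines), with no Progressive disease criterion of Appendix III a) met at the visit 9 assessment* (in the SAP, refer to Appendix 2 a).
2. Check RS_DSRESP against the recorded marrow and peripheral-blast data, and against extramedullary data if captured. The documents do not show how extramedullary disease is recorded, so confirm this first.
3. Classify patients with HI and PD at visit 9 as non-responders, list them, and report the count under the present definition as a sensitivity analysis.
4. Cross-reference or reconcile the treatment passages on continuation with HI (protocol 5.1.3, 8.1.5) and discontinuation for PD (7.7). That is for the sponsor, and no clinical rule is proposed here.

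The cost is one clause in three places and a derivation check on data mostly already scheduled. The response rate may come out slightly lower. The change would tighten the primary definition after an interim look in an open-label trial, so its date and reason should be documented. The sensitivity count keeps both results visible.

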#### **7.7.5 Overall Survival**

Overall survival (OS, in days) will be defined as the time from the beginning of treatment (date of administration at cycle ■, week ■) until date of death or censored at the date of the last observed time point alive:

In case subject dies overall survival will be:

OS [days] = date of death – Drug administration date in Visit [REDACTED] +1

Otherwise, censoring date will be:

OS [days] = Date of last observed time point alive – date of beginning of treatment +1

#### 7.7.6 Progression-free-survival

Progression-free-survival (PFS) will be defined as the duration of time from time of treatment to time of progression or death, whichever occurs first. A subject who has neither progressed (defined as first time having Progressive disease (PD) or Progression or relapse after HI on response assessment) nor died will be censored on the date of the last observation. Therefore:

In case there was a progression or death:

PFS [days] = min(date of progression/death) – Drug administration date in Visit [REDACTED] +1

Otherwise, censoring date will be:

PFS [days] = date of last observation – Drug administration date in Visit [REDACTED] +1

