2.3.2 Secondary endpoints

The following secondary endpoints will be analyzed in this study.

Safety Measurements

- Toxicity as measured by NCI CTCAE v5.0

Efficacy Measurements

- Overall survival
 - defined as the time from the beginning of imetelstat treatment until death or censored at the date of the last follow-up visit.
- Progression-free-survival
 - defined as the duration of time from time of imetelstat treatment to time of progression or death, whichever occurs first. A subject who has neither progressed nor died will be censored on the date of last follow-up visit.
- Duration of best overall response
 - measured from the time measurement criteria are met for CR, CRi, PR or SD (whichever is first recorded, defined in Appendix III a)) until the first date at which recurrent or progressive disease is objectively documented.
- Best overall response
 - defined as the best response recorded from the start of the imetelstat treatment until disease progression (taking as reference for progressive disease the smallest measurements recorded since the treatment started).
- Response based on IWG 2023 criteria²⁴ (MDS population only)
 - assessed in [REDACTED] of treatment with imetelstat as:
 - Overall Response Rate (ORR) = CR (or CR equivalent)* + PR + CR_L + CR_h + HI, or
 - No response = Not meeting criteria for CR (or CR equivalent)*, PR, CR_L, CR_h, or HI.
 - For definition see Appendix III b).
- Scores of EORTC QLQ-C30 (version 3)
 - Global health status / QoL
 - Functional scales
 - Symptom scales / items

3 Translational program

Bone marrow and blood samples will be obtained at the indicated time points and stored for translational analyses, in particular assessment of response and measurable residual disease and identification of prognostic or predictive biomarkers. If adequate BM aspirate is not attainable, peripheral blood may be used if at least 5% or more BM blasts are present. If this is not the case, a BM biopsy will be required.

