#### 7.7.7 Duration of response

Duration of response (DoR) will be measured from the time measurement criteria are met for CR, CRi, PR, MLFS or SD (whichever is first recorded, defined in section 11.2 Appendix 2 a)) until the first date at which recurrent or progressive disease is objectively documented for patients with confirmed CR, CRi, PR, MLFS or SD criteria met. Therefore:

DoR [days] = first date with PD response criteria after response – date of CR, CRi or PR response criteria +1

If there was no progressive disease documented, subject will be censored on last documented response assessment:

DoR [days] = date of last response assessment – date of CR, CRi or PR response criteria +1

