## 11.2 APPENDIX 2: Combined response assessment criteria for MDS and AML

### a) Combined response assessment criteria for MDS and AML

Based on IWG 2018 criteria (MDS) and the criteria of the European LeukemiaNet (AML)

CATEGORY	DEFINITION
Complete remission (CR)	Bone marrow blasts <5%; absence of circulating blasts and blasts with Auer rods; absence of extramedullary disease; ANC $\geq 1.0 \times 10^9/L$ (1000/ $\mu L$ ); platelet count $\geq 100 \times 10^9/L$ (100 000/ $\mu L$ )
CR with incomplete hematologic recovery (CR i )	All CR criteria except for residual neutropenia (<1.0 $\times 10^9/L$ [1000/ $\mu L$ ]) or thrombocytopenia (<100 $\times 10^9/L$ [100 000/ $\mu L$ ])
Partial remission (PR)	All hematologic criteria of CR; decrease of bone marrow blast percentage to $\geq 5\%$ ; and decrease of pretreatment bone marrow blast percentage by at least 50%
Morphologic leukemia-free state (MLFS)	Bone marrow blasts <5%; absence of blasts with Auer rods; absence of extramedullary disease; no hematologic recovery required
Stable disease (SD)	Absence of CR, CR i , PR, MLFS; and criteria for PD not met
Progressive disease (PD)	Evidence for an increase in bone marrow blast percentage and/or increase of absolute blast counts in the blood: 
 
>50% increase in marrow blasts over baseline (a minimum 15%-point increase is required in cases with <30% blasts at baseline; or persistent marrow blast percentage of >70% over at least 3 mo; without at least a 100% improvement in ANC to an absolute level (<math>>0.5 \times 10^9/L</math> [500/<math>\mu L</math>], and/or platelet count to <math>>50 \times 10^9/L</math> [50 000/<math>\mu L</math>] non-transfused); or
 
>50% increase in peripheral blasts (WBC <math>\times</math> % blasts) to <math>>25 \times 10^9/L</math> (<math>>25</math> 000/<math>\mu L</math>) (in the absence of differentiation syndrome)†; or
 
New extramedullary disease
 

Hematologic relapse (after CR, CR i )	Bone marrow blasts ≥5%; or reappearance of blasts in the blood; or development of extramedullary disease
Hematologic improvement (HI)	
Erythroid response ( HI-E )	

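### The SAP's PFS event list omits hematologic relapse after CR/CRi, its DoR formula contradicts its own DoR text, and death is not a DoR event

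*SAP*

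**What the plan says.** **PFS.** Protocol 2.3.2 has PFS "defined as the duration of time from time of imetelstat treatment to time of progression or death, whichever occurs first" and does not tie progression to particular response categories. SAP 7.7.6 does: progression is "defined as first time having Progressive disease (PD) or Progression or relapse after HI on response assessment". A patient who has not progressed in this sense "nor died will be censored on the date of the last observation".

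**Response categories.** SAP Appendix 2 a), which repeats Protocol Appendix III a), lists three kinds of failure: PD, progression or relapse after HI, and hematologic relapse after CR or CRi. The last is met by marrow blasts of 5% or more, "or reappearance of blasts in the blood; or development of extramedullary disease". PD by marrow blasts needs a rise of more than 50%, worded as an "increase in marrow blasts over baseline (a minimum 15%-point increase is required in cases with" a baseline below 30%.

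**DoR.** Protocol 2.3.2 measures response "until the first date at which recurrent or progressive disease is objectively documented", and the text of SAP 6.2.2 and SAP 7.7.7 says the same. The formula under that text in 7.7.7 ends at the "first date with PD response criteria after response". The censoring rule reads: "If there was no progressive disease documented, subject will be censored on last documented response assessment". The 7.7.7 text starts the clock at CR, CRi, PR, MLFS or SD, while the formula starts it at CR, CRi or PR. Protocol 2.3.2 lists CR, CRi, PR or SD. Neither document mentions death for DoR.

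**Reference for PD.** The best-overall-response definition (Protocol 2.3.2, SAP 6.2.2) judges PD against the smallest value since treatment start. The PD row of the appendix uses baseline.

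**The concern.** SAP 7.7.6 names relapse after HI but not relapse after CR or CRi, so its list cannot be read as shorthand for every kind of failure. Read literally, the patients with the deepest responses have no failure event of their own. A patient can lose a CR, stop treatment for loss of response, and enter the PFS analysis as censored.

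For DoR, the programmer has two instructions that give different end dates for the same patient. SAP section 1 says the document is to guide statistical programming, so the formula is the version likely to be coded. Leaving death out of the events adds a second way for DoR to look longer than the time patients spend alive and in response.

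Both endpoints are reported by treatment cohort (SAP 8.4). The SAP document history records no responders at the interim analysis, so any CR or CRi will fall mainly in the later cohort. A loose rule would then favour that cohort in a descriptive comparison.

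**Working it through.** The documents give no figure to reproduce here. The check compares definitions, then does some arithmetic.

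**1. Event lists side by side**

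| Failure | PFS, SAP 7.7.6 | DoR, text of 7.7.7 | DoR, formula of 7.7.7 |
|---|---|---|---|
| PD | event | event | event |
| Progression or relapse after HI | event | not named | not an event |
| Hematologic relapse after CR/CRi | not listed | event (recurrence) | not an event |
| Death | event | not mentioned | not mentioned |

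**2. Does marrow-blast PD fill the gap?** Let b be baseline marrow blasts in percent.

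- If b < 30, PD needs max(1.5b, b + 15). This equals b + 15, because 0.5b < 15.
- If b ≥ 30, PD needs more than 1.5b.

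| Baseline b | Relapse from CR at | PD by marrow blasts at |
|---|---|---|
| 5% (lowest admitted, inclusion criterion 8) | 5% | 20% |
| 10% | 5% | 25% |
| 20% | 5% | 35% |
| 29% | 5% | 44% |
| 40% | 5% | above 60% |

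Example: baseline 12%, CR at 3%, then 20%. This is hematologic relapse (20 ≥ 5) but not marrow-blast PD (12 + 15 = 27).

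**3. Would PD be recorded later?** Loss of response ends treatment (Protocol 5.1). The Part 3 schedule for EOT and follow-up has no row for response assessment, local marrow cytology or peripheral blasts. Marrow is drawn at EOT for central analyses only, and only if more than 90 days have passed since the previous procedure. PD may therefore never be documented, and the last observation used for censoring can fall after the relapse.

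**4. Would the smallest value as reference cure it?** Not for baselines below 30%. With a smallest value of 3%, PD would start at 3 + 15 = 18%, so relapses from 5% to under 18% would still be missed.

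**5. Death in DoR.** Let d be the share of responses that end in death without documented PD, with constant hazards. The median with both events is ln 2/(h_PD + h_death). With death censored it is ln 2/h_PD. The ratio is (h_PD + h_death)/h_PD = 1/(1 − d).

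- d = 0.30: 1/0.70 = 1.43
- d = 0.50: 1/0.50 = 2.0

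The documents give no value for d.

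**6. Illustration of the relapse gap, all rates assumed.** CR at day 113, no deaths in remission, 90 days of observation after relapse, and median 120 to 168 days from relapse to death. Results are median days among patients in CR.

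| Median time to relapse | PFS, relapse an event | PFS as in 7.7.6, half of relapses meet PD | PFS as in 7.7.6, a quarter meet PD |
|---|---|---|---|
| 90 days | 203 | 276–290 | 339–377 |
| 180 days | 293 | 403–427 | 501–558 |

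Under the PD-only DoR formula, with half of relapses meeting PD, median DoR goes from about 91 to 181 days and from about 181 to 359 days. These figures describe CR patients only, not a whole cohort.

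**The case against.** **The DoR text already covers relapse.** This stands. A reader might infer that the plan does not count relapse in DoR at all. The text in SAP 7.7.7, SAP 6.2.2 and Protocol 2.3.2 all ends response at recurrence as well as progression. Only the SAP formula and censoring rule narrow it, so the defect is a contradiction.

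**PD and other events catch some relapses.** This also stands. New extramedullary disease is itself PD. So is a rise of more than 50% in peripheral blasts to above 25 × 10⁹/L. CR and HI can coexist: a patient who starts with platelets of 21 to 70 × 10⁹/L and reaches CR (at least 100) has gained at least 30, which meets the HI-P count increment. A later 50% platelet fall is then a listed PFS event. Death remains a PFS event. It would be wrong to infer that every relapse from CR is censored; the gap exists only when none of these occurs.

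**Death in DoR is a design choice.** It is true that the SAP does not depart from the protocol here, since neither makes death an event. But the effect on DoR is then left unstated.

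**Little is at stake.** Protocol 10.1 makes all analyses exploratory, the interim found no responders, and PFS is summarised by cohort rather than among responders. This limits the size and priority of the point. It does not make the event list right.

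**Conclusion.** The point holds in a conditional form. As written, SAP 7.7.6 censors as progression-free a patient who relapses from CR or CRi below the PD threshold, provided no other PD criterion is met, no earlier HI is lost and no death is observed. SAP 7.7.7 contradicts itself on both the end and the start of DoR. Under both documents, a patient who dies without documented PD is censored for DoR at the last response assessment.

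The direction is toward longer PFS and DoR, but the size is unknown. It depends on how many patients reach CR or CRi, how many relapses also meet PD, and how many responses end in death. A reader might take 1.4-fold or 2-fold as the expected inflation. The documents do not support that, because the death shares and the constant hazards behind those factors are assumptions. Nor do they show that a cohort's median PFS would move materially.

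This should be fixed before database lock, as a correction to exploratory secondary endpoints.

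**What to change.** - **SAP 7.7.6:** define the PFS event as the first of PD, hematologic relapse after CR/CRi, progression or relapse after HI, or death.
- **SAP 7.7.7, end of response:** make the formula and censoring rule match the text, so that PD and hematologic relapse after CR/CRi both end DoR.
- **SAP 7.7.7, start of response:** align the formula's start categories with the text, and carry the same list into Protocol 2.3.2, which does not name MLFS.
- **Death:** count it as a DoR event, or at least report DoR with death as an event alongside, with matching words in Protocol 2.3.2.
- **Reference for PD:** the best-overall-response definition and the appendix PD row contradict each other and must be reconciled. PD also governs stopping treatment (Protocol 7.7), so no choice is proposed here.

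The cost is SAP text, derivation code and a short protocol wording change. No new data are needed, and SAP 2.10 provides for SAP updates before database lock. The added events either bring a failure forward or turn a censored time into a failure, so they work toward shorter PFS and DoR, by an amount that depends on how many patients reach CR or CRi. Aligning the start list is a separate matter: it admits patients with SD or MLFS and can start the clock earlier, so its effect on DoR could go either way.
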